6.3.2. Unsolicited Adverse Events

Unsolicited AEs will be captured at study visits and by a diary distributed to participants. Diaries for unsolicited AEs will be reviewed at all study visits until 30 days after the last dose of vaccine. A sample diary for the recording of unsolicited events is provided in [Appendix 2](#).

6.4. Follow-Up for Disease History

Participants will be followed for self-reported SARS-CoV-2 exposure, symptoms of COVID-19 disease, and any outside test results for SARS-CoV-2 infection at study visits. Participants with symptoms of COVID-19 should be encouraged to seek testing and care, if appropriate, from their usual provider.

6.5. Clinical Laboratory Procedures and Evaluations

A list of the laboratory assessments that will be conducted during the study is provided in [Table 9](#).

Table 9: Laboratory Assessments

Chemistry ^a	Hematology ^b	Urinalysis
Albumin	WBC	Protein
ALP	RBC	Glucose
ALT	Platelets	Presence of RBCs
AST	Hemoglobin	
Calcium	Hematocrit	
Chloride	Basophils	
Creatinine	Eosinophils	
Glucose	Lymphocytes	
Phosphorus	Monocytes	
Potassium	Neutrophils	
Sodium		
Blood urea nitrogen (BUN) or urea ^c		
Uric acid		

ALT, alanine aminotransferase; AST, aspartate aminotransferase; ALP, alkaline phosphatase; BUN, blood urea nitrogen; CRP, C-reactive protein; IL-6, interleukin-6; RBC, red blood cells; TNF- α , tumor necrosis factor alpha; WBC, white blood cells.

^a A comprehensive metabolic panel (CMP) may be used to obtain chemistry assessments, provided all assessments listed above are included.

^b A complete blood count (CBC) with differential may be used to obtain hematology assessments, provided all assessments listed above are included.

^c BUN or urea should be assessed per institutional standards. Only one of the two tests is required.

6.6. Laboratory Procedures and Evaluations for Immunological Endpoints and Other Laboratory Procedures and Evaluations

Blood and other biospecimens (eg, NP swabs) will be collected at various times during this study, and shipped to the Immunity Bio laboratory. Any residual specimens collected and not shipped will be stored at the laboratory at the Wits VIDA clinic based at Chris Hani Baragwanath Academic Hospital within South Africa. If there are any extra samples remaining of shipment to the United States of America, these will be stored at ImmunityBio's laboratory in Torrey Pines, California. Samples will be stored for a maximum period of 15 years and participants will be requested to sign a separate, optional storage informed consent form in order to agree to sample storage

A brief summary of the laboratory procedures and evaluations to be performed with these samples is provided in the following sections.

6.6.1. Immunogenicity Assessments

6.6.1.1. Cellular and Humoral Response to SARS-CoV-2 Proteins

Whole blood samples for immunology analysis will be collected prior to vaccine administration and during follow-up visits as designated in the study schedule. Blood samples will be stored in a laboratory to be determined.

Binding antibody ELISAs will be used to assess anti-spike IgG antibodies. Validated cPass ELISA-based assays will be used to assess neutralizing antibodies against SARS-CoV-2. In the phase 2 randomized study, the laboratory analyses will be performed blind to participants' vaccine treatment on study.

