3. INVESTIGATIONAL PLAN

3.1. Study Design

This is a phase 1/2 open-label study assessing the safety, reactogenicity, and immunogenicity of saRNA COVID-19 boost vaccines in participants that have been previously vaccinated against or previously infected with COVID-19. Participants enrolled will include individuals previously vaccinated against COVID-19 or previously infected with COVID-19 > 3 months prior to enrollment. Previously unvaccinated/vaccinated status and previously uninfected/infected status will be established by medical history and by SARS-CoV-2 serology assessed in the prescreening visit.

The phase 1 study is a single arm, open-label study. The phase 2 is a randomized open-label study. For the phase 2 study, laboratory analyses of immunogenicity assessments will be performed blind to participants' vaccine treatment on study. In all study phases, SARS-CoV-2 serological status will be assessed in a prescreening visit.

Participants will be ≥ 18 years of age who are healthy or have medically-stable chronic diseases. The treatment regime is described in the sections that follow. The study schema is shown in [Figure 1](#).

Phase 1

In the phase 1 study, up to 60 previously vaccinated/infected participants will be enrolled in 6 separate cohorts to receive a single vaccine boost consisting of either the AAHI-SC2 or AAHI-SC3 vaccine. Dosing schedule, mode of administration, and dosage for phase 1 are indicated in [Table 4](#).

Table 4: Phase 1 Previously Vaccinated/Infected Dosing Schedule

Phase	Cohort	Participants	Vaccine	Dosing Schedule	Dosage
PHASE 1	1A	10	AAHI-SC2	Day 1	25 μ g IM
	1B	10	AAHI-SC2	Day 1	50 μ g IM
	1C	10	AAHI-SC2	Day 1	70 μ g IM
	2A	10	AAHI-SC3	Day 1	25 μ g IM
	2B	10	AAHI-SC3	Day 1	50 μ g IM
	2C	10	AAHI-SC3	Day 1	85 μ g IM

Safety will be assessed for all participants and will include monitoring of vital signs, and incidence and severity of AEs. Blood samples will be collected for hematology and chemistry analyses and urine samples will be collected for urinalysis. Toxicities will be graded using the

Guidance for Industry: Toxicity Grading Scale for Healthy Adult and Adolescent Volunteers Enrolled in Preventive Vaccine Clinical Trials (2007).

For each cohort in phase 1, after all 10 participants have completed the toxicity assessment period, the SRC will review safety results to determine if the event warrants stopping the trial, modifying the trial, or continuing without modification.

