Solicited local and systemic reactogenicity AEs will be collected using diaries for 7 days following study intervention (ie, administration of vaccine). Unsolicited AEs will be recorded in a diary from time of vaccination until 30 days after study intervention. Medically attended adverse events (MAAEs) and SAEs will be recorded for 6 months after study intervention (related MAAEs and SAEs will be recorded at any time).

Immunogenicity analyses will be conducted by collecting serum and PBMC samples from individual participants before and after vaccinations to test for humoral- and cell-mediated immune responses. Neutralizing antibodies will be assessed.

Phase 2

In the phase 2 study, up to 120 previously vaccinated/infected additional participants will be enrolled. Participants in phase 2 will be randomized 1:1:1:1 to receive Janssen or Pfizer-BioNTech vaccine (control arm), the AAHI SC2 vaccine (experimental arm 1), or the AAHI-SC3 vaccine (experimental arms 2 and 3). Dose levels for the AAHI-SC2 and AAHI-SC3 vaccines will be as determined in the phase 1 study. Randomization will be stratified by age (18 to 55 years or > 55 years), by previous infection (previously infected or not), and by HIV status (positive or negative). Treatment arms are shown in Table 5.

Table 5: Phase 2 Previously Vaccinated/Infected Dosing Schedule

Treatment Arm	Participants	Vaccine	Dosing schedule	Dosage
Control arm	30	EUA or approved vaccine	Day 1	Per prescribing information
Experimental arm 1	30	AAHI-SC2	Day 1	TBD: As determined in phase 1 study
Experimental arm 2	30	AAHI-SC3	Day 1	TBD: As determined in phase 1 study
Experimental arm 3	30	AAHI-SC3	Day 1 and day 29	TBD: As determined in phase 1 study

In addition to dosing visits described above, all participants in all phases of the study will have follow up study visits for data collection.

The SRC will provide ongoing safety review in the phase 2 study. If a possible safety signal is detected, the SRC will determine if the event warrants stopping the trial, modifying the trial, or continuing without modification.

Solicited local and systemic reactogenicity AEs will be collected using diaries for 7 days following study intervention (ie, administration of vaccine). Unsolicited AEs will be recorded in

a diary from time of vaccination until 30 days after study intervention. MAAEs and SAEs will be recorded for 6 months after study intervention (related MAAEs and SAEs will be recorded at any time).

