8.2. Analysis Population(s)

The following analysis populations are defined:

Population	Definition
Modified Intent-to-Treat (mITT)	All randomized participants who receive at least one dose of vaccine. Participants will be analyzed according to their randomized arm.
Safety	All randomized participants who receive at least one dose of vaccine. Participants will be analyzed according to the actual study intervention received. The Safety Population will be used for all safety analyses.
Immunogenicity	All randomized participants who received at least one dose of vaccine with at least 1 valid follow-up assessment immunogenicity result. Participants will be analyzed according to the actual study intervention received. The Immunogenicity Population will be used for the phase 1 and 2 immunogenicity analyses.

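### Blinding of the immunogenicity laboratory is specified for phase 2 only, so phase 1 cohort results may be produced with product and dose known

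*Combined protocol and SAP*

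**What the plan says.** Blinded laboratory work appears in three places, each time for phase 2 alone.

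- Section 6.6.1.1 (assays): "In the phase 2 randomized study, the laboratory analyses will be performed blind".
- Section 3.1 (design): "For the phase 2 study, laboratory analyses of immunogenicity assessments will be performed blind". Section 8.3.1 (statistical approach) repeats this.

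On phase 1, section 3.1 says "The phase 1 study is a single arm, open-label study", with participants "enrolled in 6 separate cohorts to receive a single vaccine boost". Table 4 gives each cohort 10 participants, one product and one dose level. Section 3.4.1.2 makes S- and N-specific IgG, neutralising antibody and ELISpot T cell activity the phase 1 secondary endpoints. Section 8.3.1 has phase 1 results summarised by cohort, and section 8.3.3 gives GMTs with 95% confidence intervals.

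On the laboratory, section 6.6 says biospecimens are collected "and shipped to the Immunity Bio laboratory". The introduction to section 6 says laboratory work is done locally, and section 6.6.1.1 leaves the storage laboratory open.

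On the link between phases, section 3.1 says "Dose levels for the AAHI-SC2 and AAHI-SC3 vaccines will be as determined in the phase 1 study". It names no endpoint, criterion or decision-maker.

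**The concern.** In phase 1 the cohort label gives away both product and dose. If the laboratory can see it, any judgement made in producing a result, such as accepting a run, repeating it or counting spots, can be made with knowledge of dose. The resulting cohort summaries rest on 10 people each and have no concurrent control, so a small number of such judgements could colour how the doses compare.

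Open-label administration does not explain the gap. Phase 2 is also open-label, and the protocol still blinds its laboratory. The same kinds of assay are used in both phases, and the protocol gives no reason for treating them differently.

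At stake is the credibility of the phase 1 by-cohort immunogenicity summaries and, if they are used in that way, their contribution to the choice of phase 2 dose levels.

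**Working it through.** The protocol states no figure on this point, so there is none to reproduce. The main check is a comparison of the text, followed by an illustration of scale.

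**1. Scope of blinding.** Sections 3.1, 6.6.1.1 and 8.3.1 all say phase 2. Section 10.3 requires participant numbers in case report forms, but does not cover sample labels or hide the cohort from the laboratory. A lab manual is mentioned in the footnotes to Table 10 but is not available here. Result: masking in phase 1 is unspecified, and nothing in the text rules it out.

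**2. Which laboratory.** Section 6.6 points to the company's own laboratory and then introduces the procedures to be done on the samples, which makes testing there the natural reading. The section 6 introduction and section 6.6.1.1 do not fit with this. Result: the testing laboratory is not settled, but the gap is the same whichever laboratory does the work.

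**3. Link to the phase 2 dose.** Section 3.1 takes the doses from phase 1 without naming an endpoint. All phase 1 primary endpoints are safety endpoints (section 3.4.1.1). The planned cohort review covers safety results, and the only explicit route from phase 1 findings to a phase 2 dose is safety-driven, through the Safety Review Committee (section 7.8.2.1). Against that, the phase 1 secondary immunogenicity measures become the phase 2 primary endpoints (section 3.4.2.1). Result: influence on dose choice is possible but not stated.

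**4. Illustrative scale.** Cohort size n = 10 comes from Table 4. The fold change f and the number of affected results k are assumptions. If k results are each replaced by one f times higher, the mean log titre rises by k × ln(f)/10, so the GMT is multiplied by f^(k/10).

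| f | k | Multiplier | Shift in GMT |
|---|---|---|---|
| 2 | 1 | 2^0.1 = 1.07 | 7% |
| 4 | 1 | 4^0.1 = 1.15 | 15% |
| 2 | 2 | 2^0.2 = 1.15 | 15% |
| 4 | 2 | 4^0.2 = 1.32 | 32% |

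**5. Against sampling error.** The protocol gives no standard deviation. Assume a log10 SD of 0.3 to 0.6. With t = 2.262 on 9 degrees of freedom, the 95% half-width is 2.262 × SD/√10:

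- SD 0.3: 0.215 on the log10 scale, a factor of 10^0.215 = 1.6.
- SD 0.6: 0.429 on the log10 scale, a factor of 10^0.429 = 2.7.

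The illustrated multipliers of 1.07 to 1.32 lie inside these limits.

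**The case against.** The strongest reply is that phase 1 is a deliberately open-label, non-randomised safety study whose immunogenicity endpoints are secondary and descriptive. Phase 2 is randomised and immunogenicity is primary there, which could explain blinding only that phase. The neutralising assay is described as validated, and ELISA-type readouts leave less to judgement than ELISpot. No test between doses is planned, and the illustrated shifts are smaller than sampling error at 10 per cohort under the assumed SDs.

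Much of this stands, and it keeps the point small. It does not remove it. A descriptive summary can still be biased, and a confidence interval does not account for judgements made with dose known.

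Three stronger readings are tempting, and the protocol does not support them.

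- **A reader might infer that phase 1 immunogenicity determines the phase 2 doses.** No section says so, and the only route described is safety-driven.
- **A reader might infer that the sponsor's laboratory decides which runs are valid or repeated.** The protocol does not say who decides or by what rule, and it does not settle where testing is done.
- **A reader might infer that one rejected run removes a participant from the Immunogenicity Population.** Entry requires a participant "with at least 1 valid follow-up assessment immunogenicity result" (section 8.2), so another valid follow-up result would keep that participant in.

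**Conclusion.** The point holds as a cheap improvement. Laboratory blinding is specified for phase 2 only, and nothing in the available text stops those running the phase 1 assays from knowing product and dose. This leaves an avoidable possible source of bias in the by-cohort GMT and ELISpot summaries.

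The size of any bias cannot be estimated from the protocol. The 7% to 32% shifts are illustrations that rest on assumed 2- to 4-fold differences in one or two results out of 10. They do not predict that such replacements will occur. Influence on the phase 2 dose levels is possible because the selection criteria are unstated. That omission is a separate gap, which blinding the laboratory would not close.

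The conclusion covers the text available. A lab manual that already masks phase 1 samples would answer the point in practice, though the protocol should still say so.

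**What to change.** Change the blinding sentence in sections 3.1, 6.6.1.1 and 8.3.1 to: *In phase 1 and phase 2, laboratory analyses of immunogenicity will be performed blind to cohort, product and dose.* Add to the lab manual that samples carry participant number and visit only, and that run-validity and repeat decisions are fixed before the cohort key is released to the laboratory. The participant number should not itself encode the cohort.

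Assaying several cohorts in one batch should not be required, because holding samples could delay phase 1 readouts.

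The cost should be low: one sentence in three places and coded labels, using masking that phase 2 needs anyway. The drawback is that masking will be imperfect if cohorts enrol in sequence, as section 7.8.2.1 suggests by referring to later cohorts, because shipment dates may then reveal the cohort. Settling validity and repeat decisions before the key is released still helps in that case, because it leaves a record that they were made before the cohort was formally disclosed.

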6.6.2. SARS-CoV-2 Testing

Appropriate biospecimens (eg, NP swabs) will be collected for SARS-CoV-2 testing. A PCR-based test will be used to assess presence of virus.

6.6.3. HIV Testing

HIV testing will follow national guidelines. Two rapid tests will be performed. Indeterminate or discrepant results are resolved by ELISA testing at an accredited laboratory.

6.7. Study Schedule

The schedule of events are provided in [Table 10](#).

6.7.1. Screening Procedures and Evaluations

Before performing any study procedures, the Investigator will obtain written informed consent from the participant. The Investigator will not undertake any measures specifically required for the clinical study until consent has been obtained. A participant that is consented and does not meet all entry criteria will be considered a screen failure.

6.7.1.1. Medical History

At screening, the participant's medical history should be taken as per institutional standards. Otherwise, only the following medical history should be recorded in the eCRF:

- Current symptoms
- Items listed in inclusion/exclusion
- Existing medical conditions.
- Medications/procedures related to existing conditions.
- History of any prior COVID-19 symptoms.
- Vaccination history

Table 10: Schedule of Events: Previously Vaccinated/Infected Participants

Study Period	Prescreening ^a	Baseline/ Screening	Vaccine Administration and Initial Follow-Up					Extended Follow-Up		
			1	8	22	29	36	60	180	365
Study Day	-5 to -1	-5 to -1	1	8	22	29	36	60	180	365
Clinic visit number	Prescreening	Screening	1	2	3	4		5	6	7
Windows (Days)				± 3				± 7		± 14
General Assessments										
Informed consent	X	X								
Inclusion/ exclusion		X								
Demographics		X								
Medical history		X								
Tuberculosis screening ^b		X								
COVID-19 history of disease ^c		X	X	X	X	X		X	X	X
Confirm contraceptive measures		X	X			X				
Physical exam: height, weight ^d		X	X	X	X	X				
Vital signs ^e		X	X	X	X	X				
Concomitant medications		X	X	X	X	X		X	X	
Participant training on AE diaries			X							
Issue diaries for solicited AEs (phase 1 and 2 only) ^f				X			X			
Review and collect solicited AE diary (phase 1 and 2 only) ^f					X			X		
Issue diaries for unsolicited AEs				X						
Review unsolicited AE diary					X	X	X			
Collect unsolicited AE diary								X		

AAHI-SC2 and AAHI-SC3

ImmunityBio, Inc.

Clinical Trial Protocol: COVID-4.015 Version 4

Study Period	Prescreening ^a	Baseline/ Screening	Vaccine Administration and Initial Follow-Up						Extended Follow-Up		
			1	8	22	29	36	60	180	365	
Study Day	-5 to -1	-5 to -1	1	8	22	29	36	60	180	365	
Clinic visit number	Prescreening	Screening	1	2	3	4		5	6	7	
Windows (Days)			± 3					± 7		± 14	
In office AE collection			X	X	X	X		X			
Telephone follow-up							X ^g		X	X	
Vaccine Administration: Phase 1											
Cohort 1A			AAHI-SC2 (25 µg)								
Cohort 1B			AAHI-SC2 (50 µg)								
Cohort 1C			AAHI-SC2 (70 µg)								
Cohort 2A			AAHI-SC3 (25 µg)								
Cohort 2B			AAHI-SC3 (50 µg)								
Cohort 2C			AAHI-SC3 (85 µg)								
Vaccine Administration: Phase 2											
Experimental Arm 1			AAHI-SC2 (dose to be determined [TBD])								
Experimental Arm 2			AAHI-SC3 (dose TBD)								
Experimental Arm 3			AAHI-SC3 (dose TBD)				AAHI- SC3 (dose TBD)				
Control Arm			Janssen/Pfizer-BioNTech vaccine								
Laboratory Assessments											

Study Period	Prescreening ^a	Baseline/ Screening	Vaccine Administration and Initial Follow-Up						Extended Follow-Up		
			1	8	22	29	36	60	180	365	
Study Day	-5 to -1	-5 to -1	1	8	22	29	36	60	180	365	
Clinic visit number	Prescreening	Screening	1	2	3	4		5	6	7	
Windows (Days)			± 3						± 7	± 14	
Chemistry panel ^h		X				X					
Hematology ⁱ		X				X					
Urinalysis ^j		X				X					
Biospecimens for SARS-CoV-2 ^k		X	X		X	X					
Collect whole blood for immunogenicity ^l			X	X					X		
Pregnancy test ^m		X	X				X				
Collect blood for SARS-CoV-2 serology	X										
HIV testing ⁿ	X										

^a If possible, the prescreening visit should occur on the same day as and immediately prior to the screening visit.

^b A TB symptom screening questionnaire per local guidelines will be used. If screening positive on questionnaire then sputum test and chest X-ray may be done to exclude the diagnosis of TB. If TB is excluded on these tests and the investigator considers that further TB testing is not clinically indicated then the potential participant may proceed with enrollment into the study. All potential participants suspected of having or with proven TB will be linked into care at their local clinic.

^c Potential exposure to SARS-CoV-2, symptoms of COVID-19, and outside testing results for SARS-CoV-2 infection will be collected at each assessment.

^d Physical examination will be performed at screening and symptom-directed (targeted) physical examination at all other time points if indicated. Height required at baseline/screening visit only.

^e Vital signs of temperature, heart rate, blood pressure, and respiratory rate will be assessed as indicated. Temperature will be documented at each visit and subsequently if clinically indicated.

^f Solicited AE diaries will be issued on day 29 and collected on day 60 only for participants in experimental arm 3 of the phase 2 study.

^g The telephone follow-up on day 36 is required only for participants in experimental arm 3 of phase 2 that get a boost on day 29.

^h See Table 9 for information on chemistry laboratory assessments.

ⁱ Hematology to include CBC with differential (5 part).

^j Urinalysis testing will include at a minimum protein, glucose, and presence of red blood cells. Sample collection should occur prior to vaccine administration.

^k Sample collection should occur prior to vaccine administration.

^l On study days 1, sample collection should occur prior to vaccine administration. A lab manual will be provided to the sites with detailed guidance for serum and PBMC preparation, storage, and shipping. A day 1 aliquot should be stored for use, if needed, in diagnosis of suspected cases of thrombosis with thrombocytopenia syndrome.

^m Testing should occur prior to vaccine administration. Pregnancy testing at day 29 applies to phase 2 arm 3

ⁿ HIV-positive participants must have been on anti-retroviral therapy for ≥ 4 weeks and have HIV-1 viral load < 1,000 copies/mL at the time of enrollment

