3.3. Duration of Study

3.3.1. Duration of Treatment

For most participants, treatment will be confined to study day 1. For participants in experimental arm 3 of the phase 2 study, treatment will occur on day 1 and day 29.

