3.4.1.1. Primary Endpoints

- Incidence of MAAEs and SAEs through 1 week post final vaccine administration
- Incidence of MAAEs and SAEs through 30 days post final vaccine administration
- Incidence of MAAEs and SAEs through 6 months post final vaccine administration
- Incidence and severity of solicited local reactogenicity AEs through 1 week after each vaccine administration
- Incidence and severity of solicited systemic reactogenicity AEs through 1 week after each vaccine administration
- Incidence and severity of unsolicited AEs through 1 week post final vaccine administration

- Incidence and severity of unsolicited AEs through 30 days post final vaccine administration
- Incidence of abnormal changes of laboratory safety examinations
- Changes in vital signs

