7.8.2. Phase 1 Study Toxicity Study Stopping Rules

Safety will be monitored throughout the study.

In the phase 1 study, the first 7 days after vaccine administration are defined as the toxicity assessment period. The SRC will also review each treatment-related SAE and toxicity, during the toxicity assessment period and each treatment-related SAE and grade ≥ 3 AE after the toxicity assessment period, to determine if the event warrants stopping the trial, modifying the trial, or continuing without modification. In the event of a death that is suspected to be related to the treatment regimen, further enrollment will be delayed until the SRC approves continuation of enrollment in order to allow for proper review and notification to the IRB and the SAHPRA. In the event of a pause in clinical trial enrollment due to toxicity, both the SRC and the SAHPRA will be notified.

Stopping/pausing guidelines are predefined criteria that halt the conduct of a study. Toxicities that may warrant stopping of the trial, based on SAHPRA guidance and with grading scales from the Guidance for Industry: Toxicity Grading Scale for Healthy Adult and Adolescent Volunteers Enrolled in Preventive Vaccine Clinical Trials (2007) (see [Section 7.1](#)), include the following:

1. If 1 or more participants experience a Grade 4 AE ([Section 7.1](#)), vital sign or laboratory abnormality that is judged related to study vaccine, all vaccinations will be suspended until a full safety review is performed.
2. If 3 or more participants report the same or similar Grade 3 solicited AE, unsolicited AE, or clinically relevant laboratory abnormality judged related to the study vaccine, all vaccinations will be suspended until a full safety review is performed.
3. The study will be halted (no new enrollments and no further investigational product administered until a full safety review and consultation with the health authorities completed) if one of the following occurs:
 - a. One participant experiences an SAE judged related to the study vaccine, or
 - b. There is a participant death judged related to the study vaccine.

If any of the halting rules are met, vaccination of participants will be suspended until after full review of safety data by the SRC. The Investigator must inform the Sponsor and IRB if any of the halting rules are met. The Sponsor then must inform the SRC and SAHPRA.

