APPENDIX 1. SAMPLE DIARY FOR SOLICITED EVENTS

STUDY NUMBER*: _____

Patient Number*		Date of Vaccine Administration	/	/	/	*To be completed by the site		
-----------------	--	--------------------------------	---	---	---	------------------------------	--	--

Please answer all questions below daily for 7 days, beginning with day of treatment. Be sure to bring back this completed diary to your next clinic visit.

Intramuscular: Solicited local AEs	Instructions	Date / /						
1. Is there redness at the injection site?	Check:  Yes or  No If yes, measure longest diameter in cm	 Yes or  No _____ cm	 Yes or  No _____ cm	 Yes or  No _____ cm	 Yes or  No _____ cm	 Yes or  No _____ cm	 Yes or  No _____ cm	 Yes or  No _____ cm
2. Is there firmness at the injection site?	Check:  Yes or  No	 Yes or  No	 Yes or  No	 Yes or  No	 Yes or  No	 Yes or  No	 Yes or  No	 Yes or  No
3. Is there swelling at the injection site?	Check:  Yes or  No If yes, measure longest diameter in cm	 Yes or  No _____ cm	 Yes or  No _____ cm	 Yes or  No _____ cm	 Yes or  No _____ cm	 Yes or  No _____ cm	 Yes or  No _____ cm	 Yes or  No _____ cm

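### The ±3-day window lets the day 8 visit fall on days 5 to 7, before the 7-day solicited diary and the phase 1 toxicity assessment period are complete

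*Combined protocol and SAP*

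**What the plan says.** - **Time zero.** Section 3.3.1: "For most participants, treatment will be confined to study day 1". Only experimental arm 3 of phase 2 is dosed again, on day 29.
- **Diary period and return.** Appendix 1: "Please answer all questions below daily for 7 days, beginning with day of treatment", and then "Be sure to bring back this completed diary to your next clinic visit".
- **Visit and window.** In Table 10 the first clinic visit after dosing is visit 2, on day 8. The windows row shows ±3 days for the initial follow-up block. The collection row reads "Review and collect solicited AE diary (phase 1 and 2 only". Footnote f adds: "Solicited AE diaries will be issued on day 29 and collected on day 60 only for participants in experimental arm 3 of the phase 2".
- **Endpoints served.** Section 3.4.1.1 lists as a phase 1 primary endpoint "Incidence and severity of solicited local reactogenicity AEs through 1 week after each vaccine administration", with a matching systemic endpoint. Section 3.4.2.2.1 makes both secondary in phase 2.
- **Toxicity period.** Section 7.8.2, for phase 1: "the first 7 days after vaccine administration are defined as the toxicity assessment period". Under section 7.8.2.1 the Safety Review Committee (SRC) reviews each cohort once all 10 participants have completed that period.
- **Blood draw.** Table 10 has a row "Collect whole blood for immunogenicity", with marks that appear to fall on day 1, day 8 and one late visit.

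Nothing in the protocol makes the day 8 window one-sided, and nothing holds the diary back until its last entry is made.

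**The concern.** The visit at which the diary is handed in may take place before the diary period is over. A site that sees a participant on day 5 is within the protocol. If it collects the diary then, as Appendix 1 leads it to expect, it holds an incomplete record for an endpoint defined through one week.

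In phase 1 the same days make up the toxicity assessment period. The SRC's trigger for suspending enrollment in section 7.8.2.1 is a count of participants (three or more with related events of grade 3 or above) in cohorts of 10. A single missing record can therefore matter when the count is near the threshold.

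**Working it through.** The plan states no figure on this point that could be reproduced. The check is calendar arithmetic on its own dates.

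**Inputs.** Vaccination on study day 1 (section 3.3.1). Seven daily entries starting that day (Appendix 1). Nominal visit day 8 with a window of ±3 (Table 10).

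**1. Permitted visit days.** 8 - 3 = 5 and 8 + 3 = 11, so study days 5 to 11, which is seven calendar days.

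**2. Diary days.** 1 to 1 + 6 = 7.

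**3. Entries available at each visit day.**

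| Visit on day | Complete entries | Partial | Blank |
|---|---|---|---|
| 5 | 4 (days 1-4) | day 5 | days 6, 7 |
| 6 | 5 (days 1-5) | day 6 | day 7 |
| 7 | 6 (days 1-6) | day 7 | none |
| 8 to 11 | 7 | none | none |

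Three of the seven permitted days (3/7 = 43%) fall before the diary is complete. This is a share of allowed days, not a forecast of the share of participants. The worst case loses 2 of 7 whole entries (29%) plus part of a third.

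**4. Is the diary collected at day 8?** The Table 10 rows cannot settle this.
- By column position as extracted, diaries are issued on days 8 and 36 and collected on days 22 and 60.
- Issue on day 8 does not fit a diary that starts on the day of treatment. Issue on day 36 contradicts footnote f, which says day 29. The second collection mark, at day 60, agrees with footnote f. The displacement is therefore not a uniform shift.
- The Appendix 1 instruction gives the answer directly: the next clinic visit after day 1 is visit 2, day 8. Footnote f follows the same rule for the second dose. Issue is on day 29 and collection on day 60, the next clinic visit, because day 36 is a telephone contact.

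**5. Which diaries are exposed?** Only those for the first dose. The second diary in arm 3 ends on day 29 + 6 = 35 and is collected on day 60.

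**6. What else would catch a reaction on day 6 or 7?** Section 6.3.1 also has solicited events captured at visits. The next is nominally day 22, so recall would reach back 22 - 7 = 15 to 22 - 6 = 16 days. The unsolicited diary continues, but Appendix 2 asks only for symptoms not listed on the other diaries.

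**7. Alternative reading of the 7 days.** If the toxicity assessment period means days 2 to 8, a day 5 visit has seen 3 complete days of 7, and even a day 8 visit only 6.

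**8. Blood draw, if it is at this visit.** Days after dosing = study day - 1, so 5 - 1 = 4 to 11 - 1 = 10. With a -0/+3 window the range is 8 - 1 = 7 to 10.

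**The case against.** The strongest reply is that the window allows an early visit but nothing tells a site to take an unfinished diary. Sections 3.1, 6.3 and 7.2 each call for seven days of solicited events, and Appendix 1 asks for the diary in completed form. A site could see the participant on day 5 and leave the diary in place. This stands. A reader might infer that following the schedule necessarily truncates the endpoint, but the documents support only that it may.

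A reader might also infer that the participant is left with no diary at all. That is not so: the unsolicited diary runs until 30 days after the last dose and is reviewed at visits. What can be lost is the structured daily grading of the solicited symptoms, which that diary does not request.

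The SRC is partly protected. Its cohort review waits for the end of the toxicity assessment period, not for the visit, and serious and medically attended events are reported by other routes. But waiting for the period to end does not fill in days that were not recorded.

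The table reading is open to challenge. Taken by column position, first collection is at day 22 and there is no truncation. That reading also requires issue on day 8, which the diary's own start date rules out. The position of the ±3 mark itself varies between the repeated headers; it is read here as covering the whole initial follow-up block.

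On titres, a reader might infer that draws 4 to 10 days after dosing inflate the spread of the geometric mean titre (GMT) by some stated factor, or could pass for a difference between arms. The documents do not support either. They give no response kinetics and no standard deviation. The draw row sits in the same broken table. Section 3.4.2.1 names no time point for the primary titres. Arms are randomized to one schedule, and section 8.3.1 plans no statistical comparison between them.

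**Conclusion.** The point holds as an unreconciled overlap between three stated rules: the day 8 window, the 7-day diary and, in phase 1, the 7-day toxicity assessment period. On three of seven permitted visit days the diary cannot be complete, with up to two whole entries and part of a third missing per participant. The number of participants affected cannot be estimated, because it depends on how often sites visit early and whether they then take the diary.

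The conclusion assumes that ±3 applies to day 8 and that the first diary is returned there, as Appendix 1 implies. It matters because it touches a phase 1 primary endpoint and the record before the SRC, and because it is cheap to close. For immunogenicity, the most that can be said is conditional: if the early draw is at this visit, its timing may range from 4 to 10 days after dosing. The effect on GMTs is unknown.

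**What to change.** - In Table 10, give the day 8 visit its own window of -0/+3 days. If ±3 is a merged cell over several visits, split it and leave the others as they are.
- In section 6.3.1 and Appendix 1, state that the solicited diary is collected only once all seven daily entries are complete.
- State which calendar days the diary and the toxicity assessment period each cover, so that they and the visit window agree.

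The cost is scheduling flexibility at one visit, which falls from seven permitted days (5 to 11) to four (8 to 11), plus one line of site instruction. If the early immunogenicity draw is at this visit, the change also narrows its timing to 7 to 10 days after dosing. That is a side benefit, not the reason for the change.
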